7.3 Prior Systemic Cancer Therapies

The following prior systemic anti-cancer therapy characteristics will be summarized descriptively using the safety analysis set:

- Prior systemic anticancer therapies
 - Yes

- No
- Lines of therapy
 - 0
 - 1
 - 2
 - ≥ 3
 - n, mean, standard deviation, median, min, max
- Type of systemic therapy
 - Chemotherapy
 - Taxane therapy: Yes, No
 - Immunotherapy
 - Hormonal therapy:
 - Novel ASRI - androgen receptor antagonist
 - Novel ASRI - CYP17 inhibitor
 - GnRH analog or antagonist
 - Older general androgen receptor antagonist
 - Other
 - Targeted therapy
 - Other
- Setting of therapy
 - Neoadjuvant
 - Adjuvant
 - Advanced/Metastatic
 - Palliative
 - Other
- Disease state for which the latest therapy was given
 - Biochemical (PSA only) non-metastatic castrate sensitive
 - Biochemical (PSA only) non-metastatic castrate resistant
 - Metastatic castrate sensitive
 - Metastatic castrate resistant
- Primary reason for stopping last line treatment
 - Treatment completed
 - Progressive Disease
 - Toxicity
 - Adverse Event
 - Other
- PSA response across all prior systemic therapies
 - Sensitive
 - Resistant

Prior systemic cancer therapy information will also be provided in a data listing using the safety analysis set.

7.4 Prior Radiation Therapies

The following prior radiation therapy characteristics will be summarized descriptively using the safety analysis set. Number and percentage with

- Any prior radiation therapy

- Total duration of prior radiation therapy (weeks): A subject may receive multiple courses of radiation therapies. The total duration is the sum of the duration of each course of radiation therapy.
- Type of radiation: Brachytherapy, EBRT, IGRT, IMRT, Implanted radioisotopes, Proton-beam, Radium-223 chloride/alpharadin, Strontium-89, Samarium-153, Other radionuclide, Other: A subject may receive multiple types of radiation therapy.

7.5 Medical History

The medical history will be coded using MedDRA 24.1.

The number and percentage of patients with conditions coded to each primary system organ class (SOC) and preferred term (PT) will be summarized using the safety analysis set. If a patient has more than one medical condition within an SOC or PT, the patient will be counted only once for the respective SOC or PT.

Data listings of all medical history records will be provided using safety analysis set.

8 PROTOCOL-REQUIRED DRUG EXPOSURE AND COMPLIANCE

Safety analysis set will be used to summarize exposure and compliance.

8.1 Study Drug Exposure

The dosing data for SRF617, Etrumadenant, and Zimberelimab will be summarized descriptively (n, mean, standard deviation, median, min, max) using the safety analysis set:

- Total number of cycles started is defined as the maximum number of treatment cycles that a patient receives each drug
- Cumulative dose (mg), including cycle 1, 2, 3, 4, and overall:
 - SRF617 (mg) is the sum of the 'Actual dose administered' that the patient receives across cycles as recorded in the **Administration eCRF**
 - Zimberelimab (mg) is the sum of the 'Actual dose administered' that the patient receives across cycles as recorded in the **Administration eCRF**
 - Etrumadenant (mg) is the sum of the 'Actual dose administered' that the patient receives across cycles as recorded in the **Administration eCRF** plus Sum of (Assigned Dose × (Number of Capsules Taken per day/Number of Capsules per Assigned Dose) ×(End Date - Start Date+1) in the **Etrumadenant Diary Information eCRF**
- Total planned dose (mg), including cycle 1, 2, 3, 4, and overall:
 - SRF617 (mg) is the sum of the 'Dose Level' that the patient receives across cycles as recorded in the **Administration eCRF**
 - Zimberelimab (mg) is the sum of the 'Dose Level' that the patient receives across cycles as recorded in the **Administration eCRF**
 - Etrumadenant (mg) is the sum of the 'Dose Level' that the patient receives across cycles as recorded in the **Administration eCRF** plus Sum of (Assigned Dose × (End Date - Start Date+1) in the **Etrumadenant Diary Information eCRF**
- Compliance is 100*(Total cumulative dose/ Total planned dose), including cycle 1, 2, 3, 4, and overall
- Actual dose intensity (mg/cycle): cumulative dose / number of cycles initiated

- Planned dose intensity (mg/cycle):
 - SRF617: The planned dose intensity is $1400 \times 2 = 2800$ mg/cycle.
 - Etrumadenant: The planned dose intensity is $150 \times 28 = 4200$ mg/cycle.
 - Zimberelimab: The planned dose intensity is 480 mg/cycle.
- Relative dose intensity (%): $100 \times (\text{actual dose intensity} / \text{planned dose intensity})$
- Number of doses missing:
 - SRF617 is the total number not administered in the **Administration** eCRF
 - Zimberelimab is the total number not administered in the **Administration** eCRF
- Number of patients with at least one dose missing for Etrumadenant
- Number of infusions interrupted, for SRF617 and Zimberelimab only

The number and percentage of patients with dose missing (not administrated), infusion interrupted, reasons for dose missing (COVID-19 Related, Other), reasons for infusion interrupted (Infusion Reaction, Adverse Event other than Infusion Reaction, Other) will be presented. The number and percentage of patients with Relative dose intensity (<50%, $\geq 50\%$ – $<80\%$, $\geq 80\%$ – $<120\%$, and $\geq 120\%$) and Compliance (<50%, $\geq 50\%$ – $<80\%$, $\geq 80\%$ – $<120\%$, and $\geq 120\%$) will be presented.

All dosing data and the above derived dosing parameters will also be presented in a data listing using the safety analysis set.

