#### 4.6. Trial Stopping Rules

The following safety stopping rule will also be applied during the Safety Lead-in: If 2 or more of these 6 patients experience a Grade  $\geq 3$  related AE (with the exception of toxicities listed in Table 4), any treatment-related toxicity that causes the participant to discontinue treatment during Cycle 1, or prolonged delay (>14 days in initiating Cycle 2 due to toxicity), the trial will be halted for SRC review.

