#### **7.4.1.2. Etrumadenant and Zimberelimab**

Dose holds of etrumadenant or zimberelimab are allowed throughout the trial for no more than 56 days. If either drug has been withheld for more than 56 days, then that drug should be permanently discontinued.

For management of drug-related toxicities, the dose of etrumadenant may be reduced up to 2 times as outlined in [Table 9](#). If further dose reduction below 75 mg is indicated, etrumadenant should be discontinued. After dose reduction, the dose may be escalated during subsequent administrations at the Investigator's discretion with Medical Monitor approval. There will be no dose reductions for zimberelimab in this trial.

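### Relative dose intensity in SAP 8.1 is calculated per cycle started, not per unit of time, so a late cycle start does not lower it and a mid-cycle stop with nothing missed does

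*SAP*

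**What the plan says.** SAP 8.1 gives "Actual dose intensity (mg/cycle): cumulative dose / number of cycles initiated". Cycles are counted drug by drug: "Total number of cycles started is defined as the maximum number of treatment cycles that a patient receives each drug". The comparator is a fixed amount per cycle: 1400 × 2 = 2800 mg for SRF617, 150 × 28 = 4200 mg for etrumadenant, and for the third drug "Zimberelimab: The planned dose intensity is 480 mg/cycle". RDI is 100 times actual over planned intensity. The section then presents "The number and percentage of patients with Relative dose intensity" in four bands: below 50%, 50 to below 80%, 80 to below 120%, and 120% or more.

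SAP 2.2 sets the cycle at 28 days. The protocol allows for cycles that run longer. The stopping rule in Protocol 4.6 names a "prolonged delay (>14 days in initiating Cycle 2 due to toxicity"). Protocol 7.4.1.2 states "Dose holds of etrumadenant or zimberelimab are allowed throughout the trial for no more than 56 days", and Protocol 7.4.1.1 sets the same 56-day limit for SRF617. Protocol 7.4 lets one drug be held while the others continue.

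**The concern.** Actual and planned intensity share a time base only if each started cycle lasts 28 days and is completed. If the next cycle starts late, the doses and the cycle count are unchanged, so the delay leaves no trace in RDI. If treatment ends part-way through a cycle, the whole cycle is charged, so RDI falls although nothing due was missed. The two errors run in opposite directions and need not cancel.

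Safety and tolerability of the triplet is a primary objective, and SAP 1.1 says the abbreviated analysis will focus on safety. Fifteen patients were treated (SAP 2), so one patient in the wrong band shifts that band by 1/15 = 6.7 percentage points. Compliance in the same section does not fill the gap: it divides the dose taken by the recorded dose level or by assigned dose over diary days, again with no elapsed time. SAP section 8 specifies no summary of treatment duration or delay.

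**Working it through.** **Inputs.** Planned amounts per 28-day cycle are 2800, 4200 and 480 mg (SAP 8.1). They reproduce exactly from the doses and schedule in SAP 2.2. The delay lengths and stop days below are assumptions, because the documents contain no patient dosing data.

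**Formulas.**
- SAP: RDI = 100 × (cumulative dose ÷ cycles initiated) ÷ planned mg per cycle.
- Time-based: RDI = 100 × (cumulative dose ÷ (exposure days ÷ 28)) ÷ planned mg per 28 days. Exposure days = last scheduled administration − first dose + one dosing interval (14 days SRF617, 1 day etrumadenant, 28 days zimberelimab). This definition is mine; the SAP has none.

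**Late cycle start, all doses given**
- SRF617, 4 cycles, one 56-day delay. SAP: 8 × 1400 ÷ 4 ÷ 2800 = 100%. Exposure is 112 + 56 = 168 days, or 6 units; 11,200 ÷ 6 ÷ 2800 = 66.7%.
- SRF617, 4 cycles, a 14-day delay before each of Cycles 2 to 4. SAP: 100%. Exposure is 112 + 42 = 154 days, or 5.5 units; 11,200 ÷ 5.5 ÷ 2800 = 72.7%.
- A single 14-day delay over 4 cycles. SAP: 100%. Exposure is 126 days, or 4.5 units; 11,200 ÷ 4.5 ÷ 2800 = 88.9%, which is in the same band.

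**Etrumadenant continues while Cycle 2 starts 14 days late**
- Days on drug: 56 + 14 = 70. SAP: 70 × 150 ÷ 2 ÷ 4200 = 125%. Time-based: 10,500 ÷ 2.5 ÷ 4200 = 100%.

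**Mid-cycle stop, no due dose missed**
- SRF617 last given on Cycle 2 Day 1. SAP: 3 × 1400 ÷ 2 ÷ 2800 = 75%. Exposure is 28 + 14 = 42 days, or 1.5 units; 4200 ÷ 1.5 ÷ 2800 = 100%.
- Etrumadenant stopped on Cycle 2 Day 7. SAP: 35 × 150 ÷ 2 ÷ 4200 = 62.5%. Time-based: 5250 ÷ 1.25 ÷ 4200 = 100%.
- For SRF617 stopped after Day 1 of cycle k, the SAP value is (2k − 1) ÷ 2k: 50%, 75%, 83.3% and 87.5% for k = 1 to 4. The distortion shrinks as cycles accumulate.

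**Where the two formulas agree**
- SRF617 Day 15 infusion skipped in a one-cycle course: 1400 ÷ 1 ÷ 2800 = 50% both ways.
- Zimberelimab, given only on Day 1: a stop at any later day of the cycle gives 100% both ways.

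**Ambiguity in the cycle count.** Zimberelimab given in Cycles 1 and 3 only reads 960 ÷ 2 ÷ 480 = 100% if two cycles are counted for that drug, and 960 ÷ 3 ÷ 480 = 66.7% if three are. The time-based value is 960 ÷ (84 ÷ 28) ÷ 480 = 66.7%.

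**The case against.** Four points can be made for the SAP.

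1. *Many holds do lower RDI.* Under Table 5 in Protocol 7.1.3, an infusion missed by more than 3 days is skipped and the schedule moves on. If the other drugs keep the cycles advancing, a held SRF617 infusion is lost inside a counted cycle and RDI falls as it should. This stands. A reader might infer that RDI never registers a delay; the documents do not support that. The fault needs a late cycle start or lengthened cycle with the doses still given, a situation that Protocol 4.6 contemplates.

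2. *Other outputs show the same events.* SAP 11.1 tabulates adverse events leading to interruption, reduction and withdrawal. SAP 6.2 gives the discontinuation reason for each drug, with progression separate from adverse events. SAP 8.1 counts missed doses and interrupted infusions and lists all dosing data. So a reader might infer that toxicity-related delay vanishes from the report, and that would be wrong. These tables count patients or doses, however, not time lost, and missed-dose reasons are only COVID-19-related or other. With 15 patients delays can be rebuilt by hand from the listing, but no specified summary shows them.

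3. *Dose per cycle is a recognisable, openly labelled convention.* It is internally consistent. It still cannot separate a delay from full dosing, or an early stop from under-dosing.

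4. *A plain time-based measure has its own blind spot.* If exposure ended one interval after the last dose given, a patient whose Cycle 2 Day 15 infusion was withheld for toxicity and who never resumed would read 3 × 1400 ÷ 1.5 ÷ 2800 = 100%, against 75% under the SAP. This stands and determines the end date in the fix.

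**Conclusion.** The point holds within limits. RDI as defined does not measure dose per unit time. It reads 100% where time-based values are 66.7% and 72.7%, 125% where no extra daily dose was taken, and 75% or 62.5% where nothing due was missed. Each of these five examples puts the patient in a different reporting band from the time-based value. Shorter delays over more cycles may not: one 14-day delay in four cycles does not.

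The delay results assume that the cycle clock pauses and all doses are eventually given. The 125% result assumes etrumadenant is taken daily throughout. The mid-cycle error concerns SRF617 and etrumadenant only. How often any of this occurred cannot be known from the documents.

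A reader might infer that the trial's safety or efficacy conclusions are compromised. The documents do not support that: the primary safety endpoint is the incidence and severity of adverse events, RDI is descriptive, no test or decision rule uses it, and the primary response result is untouched. It should be corrected because the remaining analysis centres on safety in 15 patients.

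**What to change.** In SAP 8.1, add a time-based RDI, either alongside the per-cycle value or as the one that is categorised: cumulative dose ÷ (exposure days ÷ 28) ÷ planned dose per 28 days, keeping 2800, 4200 and 480 mg. Run exposure from the first dose to the last scheduled administration, whether given or recorded as not administered, plus one dosing interval (14, 1 and 28 days for SRF617, etrumadenant and zimberelimab). For etrumadenant use the last diary date, including recorded missed doses. State how a cycle in which a drug was wholly held is counted in the per-cycle value. Also summarise treatment duration.

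With this end date, a Cycle 2 Day 15 SRF617 infusion withheld and never resumed gives 42 + 14 = 56 days, or 2 units, and 4200 ÷ 2 ÷ 2800 = 75%, so it still counts as under-dosing. A stop with no dose missed reads 100%.

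The cost is a little extra programming from dates and not-administered records that SAP 8.1 already draws on. Reported values will move in both directions. One limit remains: a permanent stop for toxicity before the next dose is due still reads 100%, so the table must be read with the summary of adverse events leading to withdrawal in SAP 11.1.

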9 PRIOR AND CONCOMITANT THERAPIES

Safety analysis set will be used to summarize prior and concomitant therapies.

9.1 Prior and Concomitant Medications

Prior and concomitant medications will be coded using WHODrug-Global-B3 September 2021 with Anatomical Therapeutic Chemical Classification System (ATC) and preferred names (PN). Prior medications include non-study drug medications that are ended before Day 1. Concomitant medications include non-study drug medications that are used on/after Day 1.

The number and percentage of patients with prior medication or concomitant medications will be summarized by ATC level 2 category and preferred name (PN). If a patient received more than 1 drug within an ATC class or PN, the patient will be counted only once for this ATC class or PN. Prior and concomitant medications information will also be provided in a data listing.

9.2 Prior and Concomitant Procedures

Prior and concomitant procedure information will be provided in a data listing.

10 EFFICACY ANALYSIS

The assessment of tumor response is based on PCWG3 criteria as well as RECIST v1.1 being evaluated by Investigators. The summary will be presented using response-evaluable analysis set.

Assessment of response will be evaluated by computed tomography or magnetic resonance imaging of chest/abdomen/pelvis and bone scan every 12 weeks. PSA assessment will be performed every cycle. Patients should continue past PSA progression until clear radiologic progression or clinical progression (eg, symptomatic or physical deterioration in the absence of radiographic progression that meets PCWG3 criteria). The overall PCWG3 criteria and RECIST v1.1 Response visit responses include Complete Response (CR), Partial Response (PR), Stable Disease (SD), Progressive Disease (PD), Non-CR/Non-PD, Not Evaluable (NE), Not Assessed (NA),

10.1 Definitions of Efficacy-related Variables

10.1.1 Best Overall Response

The best overall response (BOR) will be derived from all of visit overall responses per patients, including CR, PR, SD, PD, NE. Initial assessment of CR or PR per PCWG3 criteria or RECIST v1.1 needs to be confirmed by a second scan performed at least 4 weeks later. Unconfirmed CR or PR will be categorized as SD. Non-CR/Non-PD will be considered as SD and NA will be considered as NE during derivation. The patients in response-evaluable analysis set without any visit overall response will be categorized as NE. RECIST 1.1 BOR and PCWG3 BOR will be derived separately. Disease assessments after the start of new anticancer therapy will be excluded from efficacy derivation.

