## **6.3. Response Assessment Procedures**

For all parts of the trial, response and progression will be determined by Investigator assessment at the time points shown in [Table 2](#) as compared with Baseline tumor evaluation (see Section [6.1.10](#)) performed in Screening assessments ([Table 1](#)). The modality chosen to evaluate each individual patient should be the same throughout the duration of the trial. Redacted images may be collected.

Of note, for patients who achieve a CR or PR, a follow-up response assessment should be performed after at least 4 weeks to confirm the response. Patients will be expected to continue to follow the response assessment schedule as outlined in the Schedules of Assessments.

These evaluations will be conducted until the patient experiences progressive disease or discontinues the trial. See Section [6.3.1](#) for more information regarding the response procedures and response criteria.

Note that pseudoprogression or initial progression followed by clinical benefit/response may occur in patients treated with immune-modulating agents; therefore, treatment past progression may be considered if the Investigator and Sponsor agree and the patient is otherwise clinically stable and believed to be deriving clinical benefit. Patients who remain on trial past initial radiologic progression should have repeat imaging within 4 to 8 weeks.

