### **6.3.1. Response Evaluation Criteria**

PCWG3 criteria will be applied at the time points specified in the Schedules of Assessments ([Table 2](#)). Assessment of response will be evaluated by computed tomography or magnetic resonance imaging of chest/abdomen/pelvis and bone scan every 12 weeks. PSA assessment will be performed every cycle. Patients should continue past PSA progression until clear radiologic progression or clinical progression (eg, symptomatic or physical deterioration in the absence of

radiographic progression that meets PCWG3 criteria). If osseous disease is present at Baseline, disease assessment will follow the 2+2 rule to discriminate between flare and true progressive disease in bone lesions. The Screening bone scan will be used as the Baseline scan. Patients will be permitted to continue on study drug past progression if the Investigator feels the patient is otherwise experiencing clinical benefit and Sponsor agrees (see Section 6.3). However, if a repeat scan 4 to 8 weeks after initial progressive disease confirms additional progression per PCWG3 criteria, the patient should discontinue study drug(s).

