## 9.5. Efficacy Analyses

ORR will be assessed separately by PCWG3 criteria as well as RECIST v1.1. The primary response endpoint is defined as the proportion of patients achieving PSA50 and/or radiographic objective response of CR/PR measured using PCWG3 criteria. PSA response (PSA50) is defined as a confirmed PSA decrease from Baseline of 50% or more based on 2 consecutive assessments measured 3 to 4 weeks apart. Changes in PSA across the trial period will be described using a waterfall plot. Swimmer plots will be used to describe time on trial, including timing and incidence of treatment past progression and timing of SAEs or AESIs, and may be used to reflect the concept of no longer clinically benefiting.

For efficacy endpoints derived from progression and/or response status, disease assessments after the start of new anticancer therapy will be excluded from consideration.

The number and percentage of patients with best overall response per PCWG3 criteria and per RECIST v1.1 in each of the response categories will be presented. ORR will be estimated by the percentage of patients achieving a best overall response of CR or PR. The estimated ORR along with the 2-sided 80% and 95% exact CIs will be provided.

Time-to-event endpoints such as the following will be summarized and estimated via the Kaplan-Meier method if the number of events is adequate:

- DoR, defined as the time from the first documented response (PSA50 and/or CR/PR) to documented disease progression as determined by applicable disease criteria, or documented death due to any cause, whichever occurs first. PSA50 and objective responses (CR or PR) will also be assessed individually.
- DCR, defined as the percentage of patients with CR, PR, or stable disease lasting a minimum of 12 weeks
- PFS, defined as the time from the first treatment on trial with study drug to documented disease progression as determined by applicable disease criteria or death
- Landmark PFS, defined as the percentage of patients who have not developed PFS events (ie, death or documented disease progression as determined by applicable disease criteria) at 6 months, 12 months, 18 months, and 24 months
- Time to PSA progression
- Time to radiologic progression

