10.1.3 Primary Composite Response Rate

The primary composite response rate (PCRR) is defined as the proportion of patients achieving PSA₅₀ and/or radiographic objective response of confirmed CR/PR measured using PCWG3 criteria.

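### SAP 10.1.1 does not stop best overall response at first documented progression, so a confirmed CR/PR first reached after PD would count in the primary composite response

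*SAP*

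**What the plan says.** SAP 10.1.1 begins: "The best overall response (BOR) will be derived from all of visit overall responses per patients". Two limits follow. The first is confirmation, under both sets of criteria: an initial response finding "needs to be confirmed by a second scan performed at least 4 weeks later. Unconfirmed CR or PR will be categorized as SD". The second limit is a cut-off in time: "Disease assessments after the start of new anticancer therapy will be excluded from efficacy derivation". Protocol 9.5 has the same single cut-off for endpoints built on response or progression status: "disease assessments after the start of new anticancer therapy will be excluded from consideration". Neither document ends the derivation at first documented PD. Protocol Appendix 3 defines lesion response and time-point response and gives no rule for best response.

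SAP 10.1.3 defines the primary composite as PSA50 and/or "radiographic objective response of confirmed CR/PR measured using PCWG3 criteria". It does not name BOR, but 10.1.1 is the only place where a confirmed CR/PR is derived. SAP 10.2.1 reports the composite with exact 80% and 95% intervals and a one-sided exact p value against 10%.

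Protocol 6.3 foresees pseudoprogression and response after initial progression. It says that "treatment past progression may be considered if the Investigator and Sponsor agree and the patient is otherwise clinically stable", and it asks for repeat imaging at 4 to 8 weeks in patients who stay on trial past radiologic progression. Section 6.3.1 adds, subject to Sponsor agreement: "Patients will be permitted to continue on study drug past progression if the Investigator feels the patient is otherwise experiencing clinical benefit". Routine response assessments otherwise run until PD or trial discontinuation (Protocol 4.7, 6.3 and the Table 2 footnote on response assessments).

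**The concern.** The protocol expects that some patients may be imaged and treated after progression and that some of them may then respond. The SAP does not say how to classify those responses. Its rule takes every visit response, so it counts them. The same criteria would then have called the patient progressed at one visit and a primary responder on later ones, with no immune-modified response criteria adopted to justify it.

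The composite is the only efficacy rate that SAP version 2.0 still summarises. It comes from an open-label, single-arm trial with Investigator assessment and is tested against a fixed 10%. A rule that can add responders but never remove them should be a deliberate, stated choice.

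**Working it through.** **The plan's own figure.** Inputs from Protocol 9.1 and SAP 2.3: 17 patients, then 23 more; success at 8 or more of 40; rates 10% and 30%. Take the Stage 1 rule as 2 or more responses of either kind, which simplifies the stated rule. The probability of success is then the sum over x = 2 to 17 of b(17, x, p) × P(Y ≥ 8 − x), with Y binomial(23, p). This gives 0.0399 at p = 0.10 and 0.934 at p = 0.30, against the stated 0.040 and 0.93. The design figures reproduce, and nothing in this point changes them.

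**Whether the path exists in the text.** Take a patient with PD at the first scheduled scan.

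1. Week 12: target-lesion sum at least 20% above its smallest value, with the required 5 mm absolute increase (Table 14). Visit response PD.
2. Treatment continues with Investigator and Sponsor agreement. Repeat scan 4 to 8 weeks later, at weeks 12 + 4 = 16 to 12 + 8 = 20. If the sum is now at least 30% below Baseline and there is no new lesion, the visit response is PR.
3. Protocol 6.3 asks for a follow-up assessment at least 4 weeks after any CR or PR, so at week 16 + 4 = 20 or later. If PR persists, it is confirmed.
4. No new anticancer therapy has started, so SAP 10.1.1 excludes nothing. BOR is PR, and the patient meets 10.1.3. With a stop at first PD, BOR would be PD.

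The patient adds to the composite only if he is not already a responder by PSA50. The denominator does not change, because membership of the Response-Evaluable set (SAP 3.4) does not depend on the response obtained.

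**Size.** SAP 1.1 and 2 give 15 treated patients. Assume all 15 are response-evaluable. One added responder moves the rate by 1/15 = 6.7 points. The 95% Clopper-Pearson limits are the 0.025 quantile of Beta(x, n − x + 1) and the 0.975 quantile of Beta(x + 1, n − x). The one-sided p is P(X ≥ x) for X binomial(15, 0.10). For example, at x = 2 it is 1 − 0.9^15 − 15 × 0.1 × 0.9^14 = 0.451.

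| Responders of 15 | Rate | 95% CI | One-sided p against 10% |
|---|---|---|---|
| 1 | 6.7% | 0.2-31.9% | 0.794 |
| 2 | 13.3% | 1.7-40.5% | 0.451 |
| 3 | 20.0% | 4.3-48.1% | 0.184 |
| 4 | 26.7% | 7.8-55.1% | 0.056 |
| 5 | 33.3% | 11.8-61.6% | 0.013 |

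With fewer evaluable patients the step is slightly larger: 1/14 = 7.1 points (2/14 = 14.3% to 3/14 = 21.4%) or 1/13 = 7.7 points (2/13 = 15.4% to 3/13 = 23.1%). All responder counts are illustrations; the documents give none.

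**The case against.** The strongest reply is that the route is narrow and the trial is over. A reader might infer that any CR/PR recorded after progression counts. It does not, because an unconfirmed one becomes SD. Two post-PD scans at least 4 weeks apart, both before new therapy, must show response. Under Table 15 (RECIST v1.1) a recorded new lesion keeps the visit at PD, and PR is measured from Baseline, not from the PD scan. The 2+2 rule already separates bone flare from true progression. Treatment past progression is permitted, not required, and routine scans stop at PD, so such visits may exist but need not. Enrolment ended at 15 treated patients for business reasons, and the abbreviated analysis focuses on safety. All of this stands and limits the size. It does not close the gap, because a schedule for collecting scans is not an exclusion in the derivation.

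A second reply is that the cited response criteria may themselves fix the window for best response. That cannot be checked from these documents. What can be checked is that the SAP's own sentence takes all visits and names one cut-off.

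Three stronger readings are not supported:

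- **Clash with duration of response or PFS.** Protocol 9.5 has "DoR, defined as the time from the first documented response" up to progression, so a response after PD seems to have no duration. SAP 10.1.4 no longer summarises duration of response or radiographic PFS, so no planned table meets this conflict.
- **Wrongly opening Stage 2.** SAP 13 records that the trial ended without proceeding to Stage 2.
- **A proven bias against the 10% reference.** The documents do not say whether that 10% counted responses after progression. Only the direction of the effect on the observed rate is certain.

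**Conclusion.** The concern holds in a limited form. As written, SAP 10.1.1 counts a confirmed CR/PR first reached after documented PD as a primary response, and the protocol provides for the treatment and imaging that could produce one. The effect on the composite rate is upward or nil. On the assumption that all 15 treated patients are evaluable, it is 6.7 points for each patient who is a responder only by this route. How many there are is unknown and probably few. With so few patients, one such classification can still shift the exact p value visibly, for example from 0.184 (3/15) to 0.056 (4/15), although SAP 10.2.1 attaches no threshold to it. This is a gap in a derivation rule, not an arithmetic error, and it is worth closing because the composite is the one efficacy rate retained.

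**What to change.** In SAP 10.1.1, derive BOR by each criterion from assessments up to and including the first documented PD by that criterion, with bone PD as determined under the 2+2 rule, or before the start of new anticancer therapy, whichever is first. The radiographic component of 10.1.3 then follows from the PCWG3 BOR; say so there by name.

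Report confirmed responses first reached after PD on a separate descriptive line, outside the composite rate and its test.

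State in 10.1.3 whether radiographic PD also closes the PSA50 window. SAP 10.1.2 sets no such cut-off, and patients may continue past PSA progression, so without this sentence the two components could follow different rules by accident.

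The cost is a few SAP sentences, one table row and a possibly slightly lower rate. Sample size, alpha, power and clinical procedures do not change.
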